4. STUDY ENDPOINTS

4.1. Primary Efficacy Endpoints

There are two primary efficacy endpoints that will be evaluated in sequential order. The primary efficacy endpoints are as follows:

- 1. The change in the average 24-hour pain score from baseline to the 3-month follow-up [Day 90] obtained from the Daily Pain and Sleep Interference Diary.
- 2. The outcome of at least a 50% reduction (i.e., ≥ 50%) in the average 24-hour pain score from baseline to the 3-month follow-up obtained from the Daily Pain and Sleep Interference Diary.

The statistical hypotheses for the first primary efficacy endpoint are:

H₀: $\mu_t = \mu_p$ versus H_a: $\mu_t \neq \mu_p$, (I)

where μ_t and μ_p are the mean pain change from baseline to the 3-month follow-up for the VM202 and Placebo groups, respectively. A negative mean value indicates a reduction in the pain score, and a positive mean value indicates an increase in the pain score.

If the null hypothesis for the first primary efficacy endpoint above is rejected, then the formal statistical test will be performed for the second primary efficacy endpoint. The statistical hypotheses for the second primary efficacy endpoint are:

H₀: $p_t = p_p$ versus H_a: $p_t \neq p_p$, (II)

where p_t and p_p are the percentage of subjects with a change in the average 24-hour pain score from the Daily Pain and Sleep Interference Diary from baseline to the 3-month follow-up of a \leq -50% (i.e., a reduction of \geq 50%) for the VM202 and Placebo groups, respectively.

Since the formal statistical test for the second primary efficacy endpoint will not be performed if the null hypothesis of the first primary endpoint is not rejected, the significance level for both sets of the statistical hypotheses is not adjusted and kept at a two-sided 0.05.

4.2. Secondary Efficacy Endpoints

There are two key secondary endpoints that will be evaluated in sequential order. The secondary efficacy endpoints are

- The change in the average 24-hour pain score from baseline to the 6-month follow-up [Day 180] (3 months after the Day 90 injection) obtained from the Daily Pain and Sleep Interference Diary.
- The outcome of at least a 50% reduction (i.e., ≥ 50%) in the average 24-hour pain score from baseline to the 6-month follow-up [Day 180] (3 months after the Day 90 injection) obtained from the Daily Pain and Sleep Interference Diary.

The same method used to evaluate the two sequential hypotheses described in Section 4.1 will be applied to the secondary efficacy endpoints. Similarly, the hierarchical approach will be used for the evaluation of the outcomes from the secondary efficacy endpoints.

4.3. Exploratory Efficacy Endpoints

- The change in the average 24-hour pain score from baseline to the 9-month follow-up [Day 270] (6 months after the Day 90 injection) obtained from the Daily Pain and Sleep Interference Diary.
- The outcome of at least a 50% reduction (i.e., ≥ 50%) in the average 24-hour pain score from baseline to the 9-month follow-up [Day 270] (6 months after the Day 90 injection) obtained from the Daily Pain and Sleep Interference Diary.
- The outcome of at least a 20%, 30%, 40%, 60%, or 70% reduction in the average 24-hour pain score from baseline to the 3-month follow-up obtained from the Daily Pain and Sleep Interference Diary
- The outcome of at least a 20%, 30%, 40%, 60%, or 70% reduction in the average 24-hour pain score from baseline to the 6-month follow-up obtained from the Daily Pain and Sleep Interference Diary

- The outcome of at least a 20%, 30%, 40%, 60%, or 70% reduction in the average 24-hour pain score from baseline to the 9-month follow-up obtained from the Daily Pain and Sleep Interference Diary
- Change in VAS for Pain from baseline to the 3-month, 6-month, and 9-month follow-up; note that VAS is read by 2 different investigators at each assessment and the average of the two scores will be used for analysis
- Michigan Neuropathy Screening Instrument (MNSI) physical assessment and history changes from baseline to the 6-month and 9-month follow-up
- Change in average sleep interference score from baseline to the 3-month, 6-month, and 9-month follow-up obtained from the Daily Pain and Sleep Interference Diary
- BPI-DPN pain interference score changes from baseline to the 3-month, 6-month, and 9-month follow-up; note that an average score of BPI-DPI pain interference will be analyzed
- BPI-DPN pain severity score changes from baseline to the 3-month, 6-month, and 9-month follow-up; note that not only an overall average score of BPI-DPN pain severity but also each individual severity components (worst pain, least pain, average pain, pain now) will be analyzed
- Patient's Global Impression of Change (PGIC) at the 3-month, 6-month, and 9-month follow-up
- Semmes-Weinstein monofilament testing changes from baseline to the 3-month, 6-month, and 9-month follow-up.

4.4. Safety Outcomes

- Adverse events
- Injection site reaction assessment
- Vital signs
 - Blood pressure
 - o Weight
 - Heart rate
 - Respiration Rate
 - Temperature
- HbA1c

- Serum Chemistry and Hematology
- Retinal fundoscopy.

4.5. Other Clinical Parameters

- Nerve conduction at the 6-month and 9-month follow-up (selected sites)
- Total Tylenol (rescue medication) used during the study.

4.6. Planned Covariates

As defined in the primary analysis of the primary and secondary efficacy endpoints, the baseline pain and the randomization stratification factor (i.e., baseline use of gabapentin and/or pregabalin) with be introduced as covariates within the models.

As a separate secondary examination of the primary and secondary efficacy endpoints, three additional covariates will be introduced into the model to derive the covariate-adjusted estimates. (ref. Section 8.4.6 for additional details):

- Baseline HbA1c (\leq and \geq median)
- Gender (male and female)
- Age (<65 years and \geq 65 years).

5. SAMPLE SIZE CALCULATION

Table 2 provides the summary statistics for the corresponding efficacy endpoints based on change in the average pain score for the low dose and placebo groups from the intent-to-treat population and efficacy groups in the Phase II study (Protocol VMDN-002, injections at Day 0 and Day 14 only).

	ľ	T	EFFICACY				
	VM202	PLACEBO	VM202	Placebo			
		Mean ((SD)				
Month 3	-2.89 (2.47)	-1.70 (1.72)	-3.03 (2.53)	-1.53 (1.76)			
Month 6	-2.58 (2.18)	-1.63 (1.75)	-2.78 (2.23)	-1.59 (1.89)			
	Percentage of Subjects with $a \ge 50\%$ Reduction						
Month 3	45.9%	23.8%	48.4%	17.6%			
Month 6	34.3%	15.0%	38.7%	17.6%			

TABLE 2. Mean and Standard Deviation of Pain Score Changes fromBaseline and the Percentage of Subjects with at Least a 50% Reduction;Low Dose versus Placebo Group in Phase II Study

The sample size for the primary efficacy endpoints was calculated based on the following assumptions:

- Based on the Phase II findings, it is assumed that the standard deviation of the pain score change from baseline will be 3.0. The true percentage of subjects with a pain reduction of ≥ 50% is assumed to be 35% and 18% for the VM202 group and placebo group, respectively.
- The statistical power is 90% for a detectable mean difference of -1.0 (i.e., mean pain reduction for the VM202 group is higher than that for the Placebo group) for Statistical Hypotheses (I) in Section 4.1 using a t-test. The statistical power is also 90% for Statistical Hypotheses (II) in Section 4.1 provided the assumptions of $p_t = 35\%$ and $p_c = 18\%$ using a chi-square test.
- The two-sided significance level is 0.05. Since a formal statistical conclusion for the second primary efficacy endpoint will not be made unless the null hypothesis of the first primary efficacy endpoint is rejected, no adjustment on the significance level is performed.
- The randomization ratio for the VM202 group and the placebo group is 2:1.

Based on the assumptions above, the sample sizes calculated for the VM202 group and placebo group are 286 and 143 subjects, respectively, for Statistical Hypotheses (I); those for Statistical Hypotheses (II) are 212 VM202 subjects and 106 placebo subjects.

Therefore, 286 VM202 subjects and 143 placebo subjects are needed with data at the 3-month follow-up for the primary data analyses. With a dropout rate of 10%, at least 477 subjects should be randomized in order to have 318 VM202 subjects and 159 placebo subjects.

6. ANALYSIS POPULATIONS

6.1. Intent-to-Treat (ITT) Population

This population includes all subjects who are randomized. In the efficacy outputs, subjects in the ITT population will be analyzed according to the randomized treatment assignment, regardless of the actual treatment administered. In the safety outputs, subjects will be analyzed using the treatment they received in the VMDN-003 study, regardless of original treatment assigned.

The **intent-to-treat (ITT) population** will include all subjects who were randomized on the VMDN-003 study.¹ The ITT population will be the primary population used for the efficacy analyses.

All baseline characteristics will be summarized based on the ITT population. The primary analyses of the primary and secondary efficacy endpoints will be based on the ITT population.

For the ITT population, entries in the Daily Pain and Sleep Interference Diary will be considered fully valid if made anytime during the 24 hour period specified in the date entry.

6.2. Safety Population

The safety population will contain all subjects who are randomized and receive at least one study drug injection. Subjects will be grouped according to the actual treatment administered, not according to their randomization assignment. Subjects treated with any

¹ Per FDA/ICH E9 Statistical Guidance, pg. 29:

[&]quot;In some situations, it may be reasonable to eliminate from the set of all randomized subjects any subject who took no trial medication. The intention-to-treat principle would be preserved despite the exclusion of these patients provided, for example, that the decision of whether or not to begin treatment could not be influenced by knowledge of the assigned treatment. In other situations it may be necessary to eliminate from the set of all randomized subjects any subject without data post randomization. No analysis should be considered complete unless the potential biases arising from these specific exclusions, or any others, are addressed."

Helixmith is aware of 7 subjects in VMDN-003 who were randomized in error (did not meet Inclusion / Exclusion criteria or who were randomized without PI oversight). These 7 subjects were subsequently withdrawn before receiving study medication and without knowledge of treatment assignment. Details are summarized in a Note-to-File, July 12, 2019, which was prepared according to Helixmith SOP QA-002.

VM202 dose will be grouped in the VM202 group; subjects never treated with any VM202 will be grouped in the placebo group.

Subjects that sign informed consent but screen fail will still be considered part of the safety population and will have their collected safety data summarized.

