The secondary efficacy endpoints will be based on the change in the average 24-hour pain score from baseline to the 6-month follow-up [Day 180] (3 months after the Day 90 injection) obtained from the Daily Pain and Sleep Interference Diary. The difference in the mean of the change in the average 24-hour pain score will be compared between the treatment group and the placebo arm to determine the treatment effect in the efficacy populations. The proportion of subjects with at least a \geq 50% reduction in the average 24-hour pain score from baseline to the 6month follow-up [Day 180] (3 months after the Day 90 injection) will be compared between the two study groups.

All other efficacy endpoints will be exploratory.

SAFETY

Any subject who receives study injections (VM202 or placebo) will be included in the safety analysis population. Adverse events (including serious adverse events, and adverse events leading to treatment discontinuation) throughout the 9-month follow-up will be described according to severity and to their relationship with the study drug and injection procedure. Descriptive statistics (N, mean, median, SD, minimum and maximum values, where applicable) will be used to characterize continuous safety parameters. Categorical variables will be summarized by counts and by percentage of subjects in corresponding categories.

All subjects will undergo testing as presented in the American Cancer Society Cancer Screening Guidelines as part of their screening to rule out cancer.

KINETICS

PHARMACO- HGF serum levels will be determined immediately pre-treatment on Day 0, immediately pre-treatment on Day 14, on Day 21, Day 60, immediately pre-treatment on Day 90, immediately pre-treatment on Day 104, Day 111, Day 150, Day 180 and Day 270.

> The number of copies of VM202 in whole blood will be determined at Day 0 (pre-injection, and 2 hours [\pm 1 hour] post injection), at Day 14 (pre-injection, and 2 hours $[\pm 1 \text{ hour}]$ post injection), Day 21, Day 60, at

Day 90 (pre-injection, and 2 hours [\pm 1 hour] post injection), at Day 104 (pre-injection, and 2 hours [± 1 hour] post injection), Day 111, Day 150, Day 180, and Day 270.

TABLE OF CONTENTS

Investi	GATOR'S AGR	EEMENT	3
STUDY S	SYNOPSIS		4
TABLE O	OF CONTENTS.		13
ABBREV	IATIONS		17
PERSON	NEL AND FACI	LITIES	19
1. Bac	CKGROUND		23
1.		Diabetic Peripheral Neuropathy	
		Pathophysiology of Diabetic Peripheral Neuropathy	
1.1		reatment Options	
1	1.2.1.		
		Medical Management	
	1.2.3.		

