6.2. ANALYSIS POPULATION

6.2.1. INTENT-TO-TREAT POPULATION (ITT)

This subset includes all subjects who were randomized on the VMDN-003 study.² All baseline characteristics will be summarized based on ITT. Subjects in the ITT will be analyzed according to original treatment assignment, regardless of actual treatment received. The primary analyses of the primary and secondary efficacy endpoints will be based on this ITT population.

SAFETY POPULATION 6.2.2.

The safety analysis population will contain all subjects who are randomized and receive at least one study injection. Subjects will be grouped according to their actual treatment received, not according to their randomization assignment (as randomized). Subjects treated with any VM202 dose will be grouped in the VM202 group; subjects treated without any VM202 will be grouped in the placebo group.

MODIFIED ITT (MITT) POPULATION

The mITT population includes all subjects randomized that meet the following:

Helixmith is aware of 7 subjects in VMDN-003 who were randomized in error (did not meet Inclusion / Exclusion criteria or who were randomized without PI oversight). These 7 subjects were subsequently withdrawn before receiving study medication and without knowledge of treatment assignment. Details are summarized in a Note-to-File, July 12, 2019, which was prepared according to Helixmith SOP QA-002.

² Per FDA/ICH E9 Statistical Guidance, pg. 29:

[&]quot;In some situations, it may be reasonable to eliminate from the set of all randomized subjects any subject who took no trial medication. The intention-to-treat principle would be preserved despite the exclusion of these patients provided, for example, that the decision of whether or not to begin treatment could not be influenced by knowledge of the assigned treatment. In other situations it may be necessary to eliminate from the set of all randomized subjects any subject without data post randomization. No analysis should be considered complete unless the potential biases arising from these specific exclusions, or any others, are addressed."

- Received at least one dose of study medication;
- Correctly completed the Daily Pain and Sleep Interference Diary at the 3-month follow-up;
- Satisfies inclusion/exclusion criteria

Subjects will be grouped based on the randomly assigned treatments, not the actual treatment received. The mITT population will be used in the sensitivity analyses for the primary and secondary efficacy endpoints.

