6.4. SUBJECT CATEGORIZATION

Screen Failure - Any subject who was consented and entered into the Screening process appropriately, but subsequently did not meet the entry criteria in order to be treated. Subjects who fail screening will not be followed for safety or efficacy assessment, and no other study procedures will be performed. Screen failures will be replaced.

Evaluable Subject - Any subject who received the study drug.

Lost to follow-up - A subject deemed to be lost to follow-up is any subject who received treatment, but who does not complete scheduled study visits. This includes those subjects who withdraw consent and refuse further study participation and all attempts to contact the subject are deemed unsuccessful.

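### SAP 6.2 adds undosed screen failures to a safety population that it and Protocol 6.2.2 limit to randomised, injected subjects

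*SAP*

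**What the plan says.** SAP 6.2 begins: "The safety population will contain all subjects who are randomized and receive at least one study drug injection". Protocol 6.2.2 gives the same rule: "The safety analysis population will contain all subjects who are randomized and receive at least one study injection". SAP 6.2 then ends: "Subjects that sign informed consent but screen fail will still be considered part of the safety population and will have their collected safety data summarized". Protocol 6.2.2 has no counterpart to that last sentence.

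Two other protocol passages bear on it. The synopsis, under Safety, says: "Any subject who receives study injections (VM202 or placebo) will be included in the safety analysis population". Protocol 6.4 says: "Subjects who fail screening will not be followed for safety or efficacy assessment, and no other study procedures will be performed".

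On treatment columns, SAP 6.1 says: "In the safety outputs, subjects will be analyzed using the treatment they received in the VMDN-003 study, regardless of original treatment assigned". SAP 6.2 says: "Subjects will be grouped according to the actual treatment administered, not according to their randomization assignment". SAP 8.5 also groups by treatment administered. SAP 6.2 adds that "subjects never treated with any VM202 will be grouped in the placebo group". The matching clause in Protocol 6.2.2 refers to subjects who were treated, but without VM202.

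SAP 8.5 takes every Safety population member into the safety analyses, which are descriptive and have no formal tests. SAP 8.5.3 and Protocol 5.3 start adverse event collection at the first injection. SAP 8.2 tabulates the Safety population, with percentages based on the number randomised, and summarises reasons for screen failure separately.

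**The concern.** One section gives two membership rules that cannot both hold. A consented screen failure does not go on to treatment, yet the last sentence of SAP 6.2 makes that person a member of a population that the first sentence reserves for randomised, injected subjects.

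Since no safety hypothesis is tested, the displayed counts and percentages are the safety evidence, and their denominator should have one definition. Someone who is never injected cannot have a treatment-emergent adverse event recorded. Counting such people can therefore enlarge a denominator but can never add to a numerator.

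**Working it through.** **1. Membership, side by side**

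| Source | Rule | Consented screen failure a member? |
|---|---|---|
| SAP 6.2, first sentence | Randomised and injected | No |
| Protocol 6.2.2 | Randomised and injected | No |
| SAP 6.2, last sentence | Consented screen failures included | Yes |
| Protocol synopsis, Safety | Injected subjects are included | Not stated; inclusion is tied to injection |
| Protocol 6.4 | No safety follow-up of screen failures | Not stated; concerns follow-up |

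The third row contradicts the first two directly. The last two rows fit poorly with it but do not contradict it.

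**2. What screen failures could contribute**

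Adverse events are recorded only from the first injection, and Protocol 4.1.1 treats new findings before dosing as medical history. A screen failure therefore contributes zero treatment-emergent events. What exists for them is screening data such as vital signs, laboratory values and fundoscopy.

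**3. Fit with SAP 8.2**

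If all 477 planned subjects were randomised and dosed and S screen failures were added, the Safety population as a share of those randomised would be (477+S)/477, which exceeds 100% for any S above zero. If that table counts only randomised subjects, its Safety count no longer matches SAP 6.2 as written. This mismatch does not depend on treatment column.

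**4. Effect on by-arm percentages**

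- *Grouped by treatment received or administered:* screen failures received nothing and have no column. The factor is 1 and the gap is 0.
- *Never-treated clause read literally:* they fall into placebo. Displayed placebo rate = r × 159/(159+S), and false gap = r × S/(159+S). VM202 percentages do not change.

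Inputs: 159 is the planned placebo group (SAP 5). S is not in the documents, so the values below are assumptions. S = 13 is a failure share of 13/(477+13) = 2.7% of those consented, taking consented as 477+S. The others come from S = 477f/(1−f), with f = 10%, 20% and 40%. Two values of r illustrate the result. The first is 69/103 = 67.0%, the Phase II rate of subjects with non-serious events pooled over all arms, because the protocol gives no placebo-only figure. The second is 3/21 = 14.3%, the Phase II placebo rate of serious events. Both are in Protocol 1.6.4.

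| Assumed S | Placebo denominator | Factor | 67.0% shown as (gap, points) | 14.3% shown as (gap, points) | (477+S)/477 |
|---|---|---|---|---|---|
| 13 | 172 | 0.92 | 61.9% (5.1) | 13.2% (1.1) | 102.7% |
| 53 | 212 | 0.75 | 50.2% (16.7) | 10.7% (3.6) | 111.1% |
| 119 | 278 | 0.57 | 38.3% (28.7) | 8.2% (6.1) | 124.9% |
| 318 | 477 | 0.33 | 22.3% (44.7) | 4.8% (9.5) | 166.7% |

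These rows apply only to the literal reading. They span assumptions and do not estimate what this trial would show.

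**The case against.** The strongest defence is that the plan read as a whole shows what was meant. SAP 6.1, 6.2 and 8.5 all sort safety subjects by treatment received or administered. The never-treated clause follows a definition that requires an injection, so in context it means injected subjects who had only vehicle. SAP 8.2 counts the populations among randomised subjects and deals with screen failures elsewhere. Any programmer would use the treated set.

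Most of this stands. It makes the reading with no by-arm effect the natural one, and SAP 8.2 shows the intended use. But none of it amends the last sentence of SAP 6.2, which says outright that screen failures are members. Using the treated set means not following that sentence, and SAP 1 requires departures from the plan to be documented in the clinical study report.

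The defence is also right about two stronger readings. A reader might infer that the synopsis and Protocol 6.4 flatly contradict the sentence. They do not: the synopsis says who is included without saying that only they are, and Protocol 6.4 limits follow-up and further procedures, which leaves room to summarise data already collected at screening. A reader might also infer that placebo event rates will be diluted. The documents do not support that: it needs the less natural reading of one clause and a screen-failure count that they do not supply.

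**Conclusion.** The contradiction is certain and rests on no number: the last sentence of SAP 6.2 cannot stand with its first sentence or with Protocol 6.2.2. As written, it puts people into the safety set who can have no recorded adverse event and who do not fit the randomised base used in SAP 8.2.

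The numerical effect is conditional. By-arm percentages do not change on the natural reading. On the literal reading, placebo adverse event percentages are multiplied by 159/(159+S), with S unknown. A reader might suspect that this could mask a VM202 harm; the direction is the opposite, since lower placebo rates make VM202 look worse. SAP 8.5.2 already limits post-injection site results to subjects injected at that visit, and follow-up vital signs and laboratory shifts use available data, so they are largely unaffected. Efficacy, type I error and power are untouched. The severity is that of a minor correction.

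**What to change.** Delete the screen-failure sentence from SAP 6.2, so that the population matches Protocol 6.2.2. If the sponsor wants the screening safety data of screen failures reported, put them in a separate, clearly labelled listing or summary with no treatment group and outside every safety denominator.

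Aligning the never-treated clause with the protocol's wording is optional tidying: once the sentence is gone, both wordings select the same subjects. The seven subjects that the SAP footnote describes as randomised in error and withdrawn undosed are already excluded by the first sentence and need no extra rule.

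The cost is one deleted sentence and, if wanted, one separate output, settled before unblinding. No new data are needed.
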